7.8 SAFETY ANALYSIS

AEs reported to be related to study procedures will be based on the enrolled set and listed. All the other safety analyses will be performed based on the TS following BI standards.

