5.2.6.2 Adverse event collection reporting

5.2.6.2.1 Adverse event collection

The Investigator shall maintain and keep detailed records of all AEs in the patient files.

The following must be collected and documented on the appropriate eCRF(s) by the Investigator:

- from signing the informed consent onwards until the individual patient's end of trial (= the EoS visit): all AEs (serious and non-serious) and all AESIs
- after the individual patient's end of trial: the Investigator does not need to actively monitor the patient for new AEs but should only report any occurrence of cancer and trial medication related SAEs and trial medication related AESIs of which the Investigator may become aware of by any means of communication, e.g. phone call. Those AEs should be reported on the BI SAE form (refer to Section [5.2.6.2.2](#)), but not on the eCRF

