6.2.1 Screening period (Visits 1a to 1c)

No trial procedures should be performed unless the patient has consented to take part in the trial. Once a patient has consented, he / she is considered to be enrolled in the trial and to have started screening. The patient should be recorded on the enrolment log and be registered in the IRT system as a screened patient. Patients who are not eligible to proceed to Visit 2 (i.e. they fail screening at either Visit 1a, 1b or 1c) should be registered as a screen failure in the IRT system and the eCRF and no further follow-up is required. Also refer to Section [3.3](#) for guidance regarding re-screening (and re-testing) during the screening period.

The screening period is defined as the period prior to randomisation and the first administration of trial medication. It consists of 3 visits (refer to [Flow Chart](#)), namely Visit 1a, Visit 1b and Visit 1c; these visits should ideally be completed within a period of 4 weeks, but a maximum of 6 weeks (-42 days will be permitted prior to randomisation (i.e. Day 1, Visit 2). There is no minimum duration for the screening period. A patient can proceed from one visit to the next within the screening period as soon as all results from the previous visit are available and if he / she remains eligible for the trial. Visit 1b and Visit 1c can be performed as separate visits, or, they can be performed on the same day. If they are performed on the same day, the gastroscopy must be performed prior to the HVPG measurement; in this setting the site can choose whether to perform the ultrasound and [REDACTED] at Visit 1b or Visit 1c.

At Visit 1a demographic information will be collected. This includes the following:

- age on the day of informed consent (in years)
- sex (male / female in order to describe the patient's sex at birth)
- for female patients: of childbearing potential yes / no in order to characterise the patient population and as a basis for contraception requirements
- ethnicity and race in order to sufficiently characterise the patient population, to support possible subgroup analyses if needed, and to support the calculation of the kidney function via the CKD EPI formula which requires a patient to be classified as black or non-black (unless not acceptable according to local regulations)

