7.2 PLANNED ANALYSES

7.2.1 General considerations

[figure not shown]
The analyses will be performed based on the following analysis sets:

- **Enrolled set (ES)** – this analysis set includes all patients having signed informed consent and who were eligible for inclusion into the trial. The ES will be used for analyses of patient disposition
- **Randomised set (RS)** – this analysis set includes all enrolled patients that were randomised to the trial medication. The RS will be used for demographic and baseline disease characteristics presentation
- **Treated set (TS)** – the treated set includes all patients who were randomised to the trial medication and were treated with at least one dose. The TS will be used for all safety analyses
- **Full analysis set (FAS)** – this analysis set includes all randomised patients who received at least one dose of trial medication and have a baseline measurement for the primary endpoint recorded. The FAS will be used for the efficacy analyses

Further analysis sets will be defined in the TSAP, if needed.

Efficacy analyses will be performed based on the planned treatment (i.e. the treatment assignment at randomisation). Safety analyses will be based on the actual treatment received at the randomisation visit.

Unless otherwise stated, baseline is defined as the latest measurement before the first trial medication intake.

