6.4 SUBJECT SETS ANALYSED

The subject sets will be used as defined in the CTP, Section 7.2.1. These include the Enrolled set (ES), Randomised set (RS), Treated set (TS) and Full analysis set (FAS).

- Screened set (SCR) – this analysis set includes all patients having signed informed consent. The SCR will be used for analyses of patient disposition.

- 
- 
- 

The discussion on all exceptional cases and problems and the decisions on the allocation of patients to populations will be made at latest at the DBLM.

In Table 6.4:1 the subject sets which are to be used for each class of endpoint are illustrated.

Table 6.4: 1 Subject sets analysed

Class of endpoint	Subject set			
	SCR	RS	TS	FAS
Disposition	X			
Primary endpoint			X	
Secondary efficacy and [REDACTED]			X	
Secondary and further safety endpoints (including liver decompensation) & treatment exposure		X		
Demographic/baseline endpoints	X			
[REDACTED]				

Handling of Treatment Misallocations in Analysis Sets

[figure not shown]
If a patient was administered incorrect treatment during the study, for efficacy analyses:

- Subjects who took incorrect treatment will be reported under their randomised treatment group. In the case of stratification error at randomisation, the subjects will be analysed according to the stratum to which they actually belong (regardless of any mis-assignment to treatment based on identification of the wrong stratum from IRT), as such an error occurs before randomization and is therefore consistent with regulatory guidance.

Then, for safety analyses, the following will be used in addition:

- If a patient is planned to receive avenciguat (i.e., randomised to either avenciguat 2 mg BID or avenciguat 3 mg BID), then patients will be reported under the planned treatment from the randomization visit for safety analyses because the overall safety profile is expected to be driven by the amount of drug received in totality over the entire treatment duration. It is not expected that the safety profile will deviate from the planned treatment regimen if the subject receives only one or two kits of the incorrect medication at only some dosing occasions.
- If a patient is planned to receive Placebo, then patients will be reported under their randomised treatment group for safety analysis if the patient was administered no

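### The listing of procedure-related AEs uses the Enrolled Set, which requires eligibility, so patients who fail screening after gastroscopy or HVPG are left out of it

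*SAP*

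**What the plan says.** SAP 7.8 assigns analysis sets in two sentences. For procedure harm: "AEs reported to be related to study procedures will be based on the enrolled set and listed". For the rest: "All the other safety analyses will be performed based on the TS following BI standards".

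The SAP does not define the Enrolled Set itself. Section 6.4 says: "The subject sets will be used as defined in the CTP, Section 7.2.1". In protocol section 7.2.1 the Enrolled Set reads: "this analysis set includes all patients having signed informed consent and who were eligible for inclusion into the trial". The Treated Set is narrower: "the treated set includes all patients who were randomised to the trial medication and were treated with at least one dose".

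SAP 6.4 also adds a Screened Set that the protocol does not have: "this analysis set includes all patients having signed informed consent. The SCR will be used for analyses of patient disposition".

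Elsewhere the protocol uses the word enrolled more broadly. Section 6.2.1 says: "Once a patient has consented, he / she is considered to be enrolled in the trial and to have started screening". Section 3.3 uses it in the same sense for the site log of enrolled patients.

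**The concern.** A listing of procedure-related AEs should show what the invasive trial procedures did to the people who had them. Protocol Table 1.4.2: 2 names the possible harms: access-site haematoma, pneumothorax, arrhythmia and contrast-induced renal injury for HVPG, and bleeding and perforation for gastroscopy. Part of this risk falls on patients who have a procedure at screening and never receive trial medication. A set that requires eligibility removes them, so the listing would describe procedure harm only in patients who passed screening.

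The two meanings of enrolled add a practical problem. A programmer who follows the defined set will exclude screen failures, while a reader who knows only protocol section 6.2.1 will assume they are included.

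**Working it through.** The plan gives no figure to reproduce. The check follows one hypothetical patient through the definitions and the planned AE outputs.

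**The patient.** Consents, has the Visit 1c HVPG, has a procedure-related AE, and the gradient is below 10 mmHg. Inclusion criterion 4 (protocol 3.3.2) requires at least 10 mmHg at Visit 1c, so this patient is ineligible because of the procedure's own result. A patient whose Visit 1b gastroscopy does not show the required varices is in the same position. Protocol 6.2.1 expressly provides for failure at Visit 1a, 1b or 1c.

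**Set membership**

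| Set | Condition | Patient included? |
|---|---|---|
| Screened (SAP 6.4) | signed consent | yes |
| Enrolled (protocol 7.2.1) | signed consent and eligible | no |
| Randomised | randomised | no |
| Treated | randomised and at least one dose | no |
| Full analysis | randomised, dosed, baseline HVPG | no |

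**Planned outputs**

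| Output | Set | Event shown? |
|---|---|---|
| Procedure-related AE listing (SAP 7.8) | Enrolled | no |
| Other AE tables and listings (SAP 7.8) | Treated | no |
| AE and SAE listing by phase, including screening (SAP 7.8.1.1) | none named; Treated by the SAP 7.8 default | not clearly |
| Disposition (SAP 6.4 and 7) | Screened | no; it counts patients, not AEs |

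The third row is the uncertain one. SAP 7.8.1.1 assigns AEs before first intake to the screening phase and plans to list them. Two things stand in the way for an untreated patient. The SAP 7.8 default puts safety output not otherwise assigned on the Treated Set. SAP Table 6.1: 1 also ends the screening phase on the day before first dose, a date this patient does not have.

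**Is the information available?** Yes, in the main. Protocol 5.2.6.2.1 collects all AEs from signing of consent, so an AE arising on the day of a screening procedure falls within collection.

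**Which meaning of enrolled governs?** SAP 7.8 names the set, and SAP 6.4 ties that set to protocol 7.2.1. The SAP's separate Screened Set of all consented patients would duplicate the Enrolled Set if both meant consent alone. The definition that requires eligibility therefore governs as written.

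**The case against.** The strongest reply is about intent. Protocol 7.2.1 puts all safety analyses on the Treated Set, and SAP 7.8 moves procedure-related AEs to a wider set. With the consent-only use of enrolled in protocol 3.3 and 6.2.1, this suggests that the authors meant to include screen failures and that the eligibility clause in 7.2.1 is the slip. That is plausible, but it does not rescue the text. The defined set is the one that will be programmed, and the conflict has to be resolved on either reading.

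A reader might infer that these complications would appear in no output at all. The documents do not establish that. The screening-phase listing names no set, and whether the Treated Set default was meant to reach a listing of pre-treatment events is open to argument. Nor are the events lost to safety surveillance: they are recorded in the eCRF, and SAEs go to the sponsor within 24 hours (protocol 5.2.6.2.2).

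A reader might also try to size the gap from an assumed screen-failure rate. With 78 randomised, 30% gives 78/0.70 − 78 = 33 patients and 50% gives 78/0.50 − 78 = 78. Neither rate is in the documents. The counts also include Visit 1a failures, who had no invasive trial procedure. Protocol 3.2 reserves HVPG for patients who reach Visit 1c, and protocol 5.2.5.2 lets a documented gastroscopy from the previous 6 months replace the one at Visit 1b. The protocol describes the HVPG complication rate as low. The relevant number is complications in patients failing at Visit 1b or 1c; it cannot be derived and could be zero.

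Two further points stand. Randomised patients have HVPG scheduled at screening, week 8 and week 24, up to 78 × 3 = 234 procedures, and these are inside the Enrolled Set. And protocol 6.2.1 requires no further follow-up after screen failure, so a complication that surfaces later may not be collected. Changing the set cannot list what was not recorded.

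**Conclusion.** The concern holds as a defect in one planned listing. Read by its own definitions, SAP 7.8 leaves out patients who had a Visit 1b gastroscopy or Visit 1c HVPG and then failed screening, and no other AE output clearly includes them. This rests on two readings: that SAP 6.4 fixes the meaning of the Enrolled Set, and that the SAP 7.8 default applies to the screening-phase listing. The first is explicit in the text. The second is the natural reading but not the only one, so the conclusion is that coverage is unclear, not that it is absent.

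The size is unknown and may be small. No endpoint, estimate, treatment comparison or safety reporting duty changes. The point is worth correcting because following the stated rule gives an incomplete account of procedure harm and the remedy costs very little.

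**What to change.** - In SAP 7.8, base the listing of procedure-related AEs on the Screened Set.
- In the Screened Set entry in SAP 6.4, add this use beside disposition.
- In SAP 7.8.1.1, name the Screened Set for the screening-phase AE listing, and state how the phase ends for a patient who is never dosed.
- Record in the SAP that the Enrolled Set of protocol 7.2.1 is narrower than the everyday use of enrolled in protocol 3.3 and 6.2.1, so that the terms are reconciled.

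The cost is a few lines of SAP text and a changed population filter for two listings. AEs are already collected from consent, so no new data and no recalculation are needed. A footnote to the listing should say that follow-up ends at screen failure, so later complications may be missing.

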7.8.1 Adverse Events

AEs will be coded with the most recent version of MedDRA coding dictionary. Patients will be analysed according to the actual treatment received.

Any clinically significant new finding in the physical examination, vital signs (blood pressure and pulse symptoms) and in the 12-lead ECG starting after visit 2 (randomization visit) will be considered as an AE and will be reported as such.

The analyses of AEs will be descriptive in nature. All analyses of AEs will be based on the number of patients with AEs and not on the number of AEs. For this purpose, AE data will be combined in a 2-step procedure into AE records.

In the first step, AE occurrences, i.e., AE entries on the CRF, will be collapsed into AE episodes if all of the following apply:

- The same MedDRA lowest level term was reported for the occurrences.
- The occurrences were time-overlapping or time-adjacent (time-adjacency of 2 occurrences is given if the second occurrence started on the same day or on the day after the end of the first occurrence).
- Treatment did not change between the onset of the occurrences OR treatment changed between the onset of the occurrences, but no deterioration was observed for the later occurrence.

In a second step, AE episodes will be condensed into AE records provided that the episodes were reported with the same term on the respective MedDRA level and that the episodes are assigned to the same treatment.

7.8.1.1 Assignment of AEs to treatment

In general, the analysis of AEs will be based on the concept of treatment emergent AEs. That means that all AEs occurring between first drug intake until 7 days (residual effect period – REP) after last drug intake will be assigned to the on-treatment period. All AEs occurring before first drug intake will be assigned to ‘screening’ and all AEs occurring after last drug intake + REP of 7 days will be assigned to ‘follow-up’ (for listings only). For details on the treatment definition, see Section [6.1](#).

If only the start date of an AE is collected (without the start time), any AE occurrence on the same day as the first avenciguat administration will be assigned to the on-treatment phase.

Drug-related AEs which will be presented as actual treatment taken at each given timepoint. AEs and serious adverse events (SAEs) assigned to the following phases: screening, each treatment group (placebo, avenciguat 2 mg and avenciguat 3 mg), post-treatment for each treatment group will be listed.

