The combination of BI 685509 with other compounds involved in the NO-sGC-cGMP pathway, such as NO-donors (e.g. nitrates), phosphodiesterase (PDE)-5- inhibitors, non-specific PDE inhibitors and sGC-simulators might further increase the risk for hypotensive episodes and potentially reactive HR increases and the severity of these effects. Based on *in-vitro* data, BI 685509 is a weak inactivator of CYP3A4 and CYP2C8. A Drug-Drug Interaction (DDI) potential with CYP3A4 substrates cannot be excluded as BI 685509 is predicted to be a weak CYP3A4 inactivator. DDI threshold dose for CYP2C8 inactivation for the CSPH indication is close to the clinically relevant dose tested in Phase II. Thus, in addition to close monitoring of AEs among patients taking CYP3A4 narrow therapeutic index / or sensitive substrates, CYP2C8 and CYP3A4 narrow therapeutic index / or sensitive substrates will also be monitored to support patient safety. Inhibitors or inducers of UGT (uridine glucuronyl transferase) enzymes (especially UGT1A1) may potentially impact BI 685509 exposures in a clinically relevant manner. BI 685509 is a substrate of P-gp (permeability glycoprotein) and OATP (organic anion transporting polypeptide)1B1/3 transporters. Co-administration of single doses of BI 685509 and the P-gp inhibitor itraconazole increased BI 685509 C_{max} approximately 1.35-fold and AUC_{0-tz} approximately 1.55-fold, which is considered not clinically relevant. OATP1B1/3 inhibition by rifampicin increased the exposure of BI 685509 after co-administration of single doses approximately 2.15-fold for C_{max} and 2.74-fold for AUC_{0-tz}, which is considered clinically relevant. Thus, OATP1B1/3 inhibitors will be restricted (refer to Table [1.4.2: 1](#) and Section [4.2.2.1](#)).

Residual Effect Period

The Residual Effect Period (REP) of BI 685509 is 7 days. This is the period after the last dose with measurable drug levels and / or pharmacodynamic (PD) effects still likely to be present.

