7.2.6 Safety analyses

Safety analyses will be descriptive in nature and follow BI standards, including (but not limited to): AEs, SAEs and AESI. AEs will be coded using the Medical Dictionary for Drug Regulatory Activities (MedDRA). Standard BI summary tables and listings will be produced. All AEs with an onset between start of treatment and end of the REP (refer to Section [1.2.1](#)) will be assigned to the on-treatment period for evaluation.

[figure not shown]
Safety analyses will be done by “treatment at onset” principle. All treated patients will be included in the safety analysis (TS). In general, safety analyses will be descriptive in nature and will be based on BI standards. No hypothesis testing is planned.

Statistical analysis and reporting of AEs will concentrate on treatment-emergent AEs, i.e. all AEs occurring between start of treatment and end of the REP. AEs that start before first trial medication intake and deteriorate under treatment will also be considered as ‘treatment-emergent’.

Frequency, severity, and causal relationship of AEs will be tabulated by system organ class and preferred term after coding according to the current version of the MedDRA at DBL.

Laboratory data will be analysed both quantitatively as well as qualitatively. The latter will be done via comparison of laboratory data to their reference ranges. Values outside the reference range, as well as values defined as clinically relevant, will be summarised. Treatment groups will be compared descriptively with regard to distribution parameters as well as with regard to frequency and percentage of patients with abnormal values or clinically relevant abnormal values.

Vital signs, physical examinations, or other safety-relevant data observed at screening, baseline, during the course of the trial and at the end-of-trial evaluation will be assessed with regard to possible changes compared to findings before start of treatment.

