4. CHANGES IN THE PLANNED ANALYSIS OF THE STUDY

There are no changes in this TSAP compared to the statistical methods described in the CTP.

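### SAP 7.8.1.1 sends every pre-dose adverse event to screening, although the protocol counts those that worsen on treatment as treatment-emergent; the conflict affects only events kept on one CRF line

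*SAP*

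**What the plan says.** Protocol 7.2.6 gives two routes into the treatment-emergent tables. The first is by date: "All AEs with an onset between start of treatment and end of the REP" belong to the on-treatment period, and protocol 1.2.1 fixes the length of the extension: "The Residual Effect Period (REP) of BI 685509 is 7 days". The second is by worsening: "AEs that start before first trial medication intake and deteriorate under treatment will also be considered as" treatment-emergent.

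SAP 7.8.1.1 restates the first route with the same window, "all AEs occurring between first drug intake until 7 days" after the last dose. It then deals with everything earlier in one sentence: "All AEs occurring before first drug intake will be assigned to" screening. Worsening is not mentioned in that section. The phase table in SAP 6.1 also separates screening from on-treatment by date alone. SAP section 4 reads: "There are no changes in this TSAP compared to the statistical methods described in the CTP".

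The SAP does use worsening in one other place. SAP 7.8.1 says that "AE occurrences, i.e., AE entries on the CRF, will be collapsed into AE episodes if all of the following apply". One of those conditions is that treatment did not change between the onsets, or that "treatment changed between the onset of the occurrences, but no deterioration was observed for the later occurrence".

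**The concern.** The two documents give different answers for the same event. The protocol counts an AE that opened before first dose and became worse on drug; the sentence in SAP 7.8.1.1 files it under screening. Because the SAP declares no change, a programmer or reader cannot tell which rule governs.

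Pre-dose AEs will exist. Protocol 5.2.6.2.1 collects them from consent, and screening can last up to 6 weeks and includes an HVPG measurement and, where needed, a gastroscopy. The potential drug effects in protocol Table 1.4.2: 1 include oedema, nausea, diarrhoea and abdominal pain, which can start mildly in screening and become more severe under a vasodilator. Such worsening is what the second protocol route is meant to catch. If it is missed, treatment-emergent counts, and counts by maximum grade, are too low.

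**Working it through.** There is no planned figure to reproduce. The check is to trace each kind of pre-dose event through both documents. The window is not in dispute: both use first dose to last dose + 7 days.

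| Case | Protocol 7.2.6 | SAP 7.8.1 and 7.8.1.1 | Agree? |
|---|---|---|---|
| (a) Worsening entered as a new CRF line after first dose | Treatment-emergent | Not merged with the pre-dose line, because the later entry is a deterioration; keeps its own onset, so on-treatment | Yes |
| (b) One CRF line with a pre-dose start date; grade or seriousness rises after first dose | Treatment-emergent through the worsening clause | Onset before first dose, so screening | **No** |
| (c) Pre-dose event with no worsening | Not treatment-emergent | Screening | Yes |

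Case (a) takes the start of dosing as a change of treatment, which fits SAP 6.1, where screening is a separate phase. The collapsing rule works on CRF entries. It decides whether two entries merge and cannot split one entry whose grade has risen, so it does nothing for case (b).

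Case (b) is also where the protocol clause has its own effect. In case (a) the new line already qualifies by its onset date. The clause adds something only when the recorded start precedes dosing, and that is the part the SAP leaves out.

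**Size.** The documents give no rate of pre-dose AEs, of worsening, or of single-line recording.

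- One patient in an arm of 26: 1/26 = 3.8 percentage points, and only in a table where that patient has no other qualifying event.
- Illustration (all rates assumed): a share p of patients carry a screening AE into treatment, a share q of these worsen, and a share s of the worsenings stay on one line. The expected number per arm is 26 × p × q × s.
- With p = 10% to 20% and q = 25%: 26 × 0.10 × 0.25 = 0.65, and 26 × 0.20 × 0.25 = 1.3. These count all worsened screening AEs (s = 1) and so are ceilings under these assumptions.
- The documents do not say whether the eCRF asks for a new line, so s may lie anywhere from 0 to 1. The range is therefore 0 to 1.3 patients per arm.

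**The case against.** The best reply is that the SAP has left something out, not reversed a rule. SAP section 3 says that the SAP builds on protocol section 7. SAP 7.8.1.1 opens with a general qualifier. SAP 7.8.1.3 points to a sponsor guideline on AE analysis that is not available here and may contain the worsening rule. Protocol 5.2.6.1.1 also asks for worsening of the underlying disease or of other pre-existing conditions to be recorded as an AE, which would move many events from case (b) to case (a). Nothing is lost from the database either, since AEs assigned to screening are still listed.

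Much of this stands as a limit on size. It does not remove the conflict. The sentence in SAP 7.8.1.1 covers all pre-dose AEs without exception, and an unseen guideline cannot be assumed to override it. The recording rule in protocol 5.2.6.1.1 does not say that an AE already open since screening needs a new line when its grade rises.

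A reader might go further and infer that hypotension, syncope or decompensation beginning in screening will drop out of the secondary safety endpoints, and that the comparison is therefore biased towards the drug. The documents do not support that. Protocol 3.3.3 excludes previous clinically significant decompensation and a history of clinically relevant orthostatic hypotension or of faints due to hypotension or of unknown origin, and the flow chart repeats the eligibility review at Visit 2. A later syncope or variceal bleed is a new event with its own onset. Worsening of permitted perihepatic ascites falls under the recording rule for pre-existing conditions. Oedema and gastrointestinal symptoms are more plausible case (b) events, but they are not secondary endpoints. That any loss would be larger in the active arms is inference; no figure in either document shows it.

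**Conclusion.** The conflict is real and confined to case (b): an AE with a pre-dose start, kept on one CRF line, that becomes more severe or serious between first dose and last dose + 7 days. The protocol counts it and SAP 7.8.1.1 does not, with no change declared. Such an AE would be missing from the treatment-emergent tables and from any safety summary restricted to on-treatment events. An effect on the hypotension, syncope and decompensation endpoints is possible but largely limited by the exclusion criteria.

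The number affected is probably small. This conclusion assumes that SAP 7.8.1.1 is programmed as written and that at least some sites record worsening by updating an existing line; the documents neither confirm nor rule out the second. The trial is descriptive with no hypothesis tests, so no inferential claim is at risk. The point is still worth settling, because a stated SAP rule contradicts the protocol on how drug-related worsening is counted, and the correction is cheap.

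**What to change.** Amend the sentence in SAP 7.8.1.1 along these lines: *AEs with onset before first intake are assigned to screening unless they deteriorate (higher CTCAE grade, or becoming serious) between first intake and last intake + 7 days, in which case they count as treatment-emergent per CTP 7.2.6.* Apply the same rule to the AE-based secondary endpoints.

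State how deterioration is identified: from a new CRF entry, or from a recorded change of grade or seriousness on an existing entry. Protocol 8.3.1 names only onset and end dates for AEs, and neither document shows that a date of worsening is collected. If it is not, count the patient as having a treatment-emergent AE without deriving an onset date, and list these cases. If the sponsor's AE guideline already contains the rule, cite it at this point in the SAP.

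The cost is a few sentences and a small derivation. Treatment-emergent counts may come out slightly higher.
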